The effect of high intensity interval vs moderate continuous endurance exercise training on program adherence

Introduction & Background

For optimal health, current Canadian physical activity guidelines recommend 150 minutes of moderate intensity or 75 minutes of vigorous-intensity endurance exercise training per week. Yet many Canadians fail to meet these recommendations apparently due to lack of time. Recently, several studies observed that very brief, repeated exercise bouts at high intensity promote similar health and exercise performance benefits as those found with moderate endurance training of much longer duration. For example, MacPherson and colleagues (2011) has compared brief, sprint vs much longer continuous endurance exercise training and found similar improvements for endurance capacity and exercise performance. Similarly, Gillen et al. (2014) found three 20 second bouts of high interval training at an all-out effort intensity elicited similar physiological benefits as to 50 minutes of moderate endurance training. Further, another recent study found short, repeated bursts of high-intensity training over 12 weeks had similar health benefits as 50 minutes of moderate endurance training (Gillen et al., 2016). The current study will follow a similar exercise training protocol as Gillen et al. (2016) however, importantly, will control exercise time (20 minutes in both groups) because it is assumed that the shorter duration in the high intensity groups of previous studies may contribute to greater program adherence rates.

Research Objectives

1. To determine whether high-intensity interval training (HIIT) group experience a greater program adherence than moderate continuous endurance exercise training (MCEET) group when matched for time commitment of 20 minutes
2. To assess whether HIIT group results in greater improvements in fat loss and endurance capacity than MCEET group

Research Hypothesis

The study hypothesizes that HIIT group will result in greater program adherence than MCEET. Also, HIIT group will result in greater improvements in fat loss and endurance capacity vs. MCEET group.

Methods

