40 healthy adults aged 19 to 35 years (20 men, 20 women) will participate in the study. Participants will be recruited from Western University and its surrounding community via university poster. Interested participants will be asked to come to the Exercise Nutrition Research Laboratory ([name]) for a face-to-face interview with the investigator and to complete Get Active Questionnaire (GAQ) that includes medical history for pre-screening eligibility. Inclusion criteria include healthy participants between the ages of 19 to 35 years who engage in physical activity less than three times per week. They must be able to run a mile, have an access to the gym as well as smart phones (such as Android, Cat phone, Google Nexus, Samsung Galaxy, iPhone, Microsoft Lumia, myTouch or Phablets) and can access to Apps (such as MyFitnessPal, Rise Up, Calorific, My Diet Coach, Yazio, On The Regimen, See How You Eat, Lost It, MyNetDiary or MyPlate). Exclusion criteria include diabetic, pregnant, individuals with a history of fainting, low and high blood pressure, heart disease, respiratory disease, migraines, heartburn, smokers, engage in physical activity

more than two times per week and answering YES to any questions from page 1 of GAQ. Eligible participants will be provided with the written informed consent.

Once completed, all participants will complete body composition testing via air displacement plethysmography (Bod Pod) pre and post intervention (week 0 and 6). Following Bod Pod measurements, participants will run a practice mile run for familiarity and will run again for measurement purposes before and after the exercise intervention to assess their endurance capacity. Time will be measured by a stopwatch. Participants will be match-paired based on their endurance capacity to either HIIT or MCEET group for five weeks. They will fill out two validated questionnaires, physical activity enjoyment scale (PACES) and exercise adherence rating scale (EARS) after the 6th, 9th and 15th session to assess their program adherence. They will be instructed not to engage in any either exercise program during the study period.

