The first week of the exercise intervention will consist of one-on-one supervised treadmill training, three times per week in the lab. From week two to five, participants will follow the same exercise program on their own at their preferred gym three times per week in order to examine free-living individuals adhere to two exercise programs. Each participant will be matched to either HIIT or MCEET group based on their timed one-mile run. The HIIT group will perform six, 20-second bouts of high intensity interval exercise separated by 2 minutes of active recovery (walking) while the MCEET group will perform 14 minutes of continuous endurance exercise at 70% Maximum Heart Rate (MHR). Both exercise protocols will include 3 minutes of warm up and cool down at a 30% MHR, for a total of 20 minutes for each treatment.

Ratings of perceived exertion (RPE; Borg CR-10 scale) will be recorded at the end of each interval for HIIT group and at 10 and 20 minutes of exercise for MCEET group on the 6th, 9th and 15th session. All participants will log their heart rate before, during, and immediately after each training session using Fitbit or a free heart rate monitor mobile App (e.g. Argos) to ensure safety and achievement of their targeted heart rate. Participants will also complete physical activity enjoyment scale (PACES) and exercise adherence rating scale (EARS) on the 6th, 9th and 15th session to assess their program adherence. To accommodate progression, training intensity will be adjusted to maintain the desired relative exercise intensity based on above measurements. Finally, no attempt will be made to modify the participants daily diet, but a 3-day food log will be collected via free mobile app (e.g. MyFitnessPal) to assess food intake for any change. Completed questionnaires and the recorded heart rate data saved on Fitbit or a mobile app will be used to confirm program adherence.

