All the collected data will be statistically analyzed by Sigma Plot 12.0 (Systat Software, San Jose, CA, USA) using a two-way analysis of variance (ANOVA), Tukey's post hoc test, and a paired t-test. Significance set at $p < 0.05$. Sample size estimates are generated with a two-way analysis of variance (ANOVA). The primary outcome variable is the program adherence, with a minimum important difference of 19.6 between HIIT (103.8 ± 9.4) and MCEET (84.2 ± 19.1 ; Thum, Parsons, Whittle & Astorino, 2017). Based on the data from Kadam & Bhalerao (2010), we calculate the pooled variance (19.1), effect size f (0.8), and Cohen's d (1.96) for the sample size estimation.

Using ANOVA, match-paired study design, a minimum of 15 participants is required for an alpha of 0.05 and 95% power. 34% of drop out rate (Linke, Gallo & Norman, 2011) will be included in addition to the minimal sample size resulting in 20 participants for each group.

References

- Gillen, J. B., Martin, B. J., MacInnis, M. J., Skelly, L. E., Tarnopolsky, M. A., & Gibala, M. J. (2016). Twelve weeks of sprint interval training improves indices of cardiometabolic health similar to traditional endurance training despite a five-fold lower exercise volume and time commitment. *PloS one*, *11*(4), e0154075.
- Gillen, J. B., Percival, M. E., Skelly, L. E., Martin, B. J., Tan, R. B., Tarnopolsky, M. A., & Gibala, M. J. (2014). Three minutes of all-out intermittent exercise per week increases skeletal muscle oxidative capacity and improves cardiometabolic health. *PLoS One*, *9*(11), e111489.
- Kadam, P., & Bhalerao, S. (2010). Sample size calculation. *International Journal of Ayurveda Research*, *1*(1), 55–57. <http://doi.org/10.4103/0974-7788.59946>
- Linke, S. E., Gallo, L. C., & Norman, G. J. (2011). Attrition and adherence rates of sustained vs. intermittent exercise interventions. *Annals of Behavioral Medicine*, *42*(2), 197.
- Macpherson, R. E., Hazell, T. J., Olver, T. D., Paterson, D. H., & Lemon, P. W. (2011). Run sprint interval training improves aerobic performance but not maximal cardiac output. *Medicine & Science in Sports & Exercise*, *43*(1), 115-122.
- Thum, J. S., Parsons, G., Whittle, T., & Astorino, T. A. (2017). High-Intensity Interval Training Elicits Higher Enjoyment than Moderate Intensity Continuous Exercise. *PloS one*, *12*(1), e0166299.

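### The plan names a two-way ANOVA for scores repeated on the same people without factors or a participant term, so the error term for both objectives is open and, read literally, wrong

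*Combined protocol and SAP*

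**What the plan says.** The analysis plan is one sentence at the end of Methods. All data are analysed "using a two-way analysis of variance (ANOVA", with Tukey's test and a paired t-test alongside, at the 5% level. The two factors, the contrast to be tested and the error term are not given. The paired t-test is not assigned to an outcome. No part of the document names a repeated-measures factor, a participant effect or a mixed model.

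Earlier paragraphs of Methods make the data repeated on the same people:

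- The two questionnaires, PACES and EARS, are completed "after the 6th, 9th and 15th session to assess their program adherence", which gives three scores per person.
- Body composition is measured "pre and post intervention (week 0 and 6", and the timed mile is run "before and after the exercise intervention to assess their endurance capacity", which gives two values per person on each.

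Objective 2 in Research Objectives is "To assess whether HIIT group results in greater improvements in fat loss and endurance capacity than MCEET group". This is a comparison of change between arms, that is, an arm-by-time contrast.

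On allocation, Methods says: "Participants will be match-paired based on their endurance capacity to either HIIT or MCEET group for five weeks". The pairing is mentioned again in the sample-size text but not in the analysis sentence.

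**The concern.** An ordinary two-way ANOVA treats every score as an independent observation. If the plan is followed that way, three adherence scores from one person count as three people. Variation between people is then under-represented in the standard error of the arm comparison, and the primary test rejects too often. For the pre/post outcomes the error runs the other way. Stable differences between people, which cancel out of each person's change, stay in the error term and hide real differences in change.

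At stake are a false claim of better adherence with HIIT and a missed difference in fat loss or endurance. If the error term is not fixed in writing, it can also be chosen after the data are seen.

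**Working it through.** **Inputs from the document.** 20 per arm, three adherence scores per person, two body-composition and mile-time values per person, alpha 0.05, power 95%, difference 19.6, printed variability 19.1, dropout 34%.

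**Assumptions.** Two-sided testing, because sidedness is not stated. Equal variances, a constant within-person correlation rho and no dropout in the error-rate calculations. The documents give no value of rho, so a range is shown.

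**1. The plan's own figure.** A paired t-test with 19.1 as the SD of the within-pair difference has standardized effect 19.6/19.1 = 1.026. Power is 94.3% with 14 pairs and 95.8% with 15, which reproduces the stated 15. Then 15 × 1.34 = 20.1, which gives 20 per group.

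**2. Error degrees of freedom on the literal reading.** Adherence: 40 × 3 − 6 cells = 114. Pre/post: 40 × 2 − 4 cells = 76. With the participant as the unit: 40 − 2 = 38 for either test.

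**3. Adherence, arm main effect.** The true variance of an arm mean over three scores is (1 + 2·rho) times the variance that the independent-errors model assumes. Hence

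size = 2[1 − Φ(1.96/√(1 + 2·rho))].

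| rho | 1 + 2·rho | size by formula | simulated, 20 per arm |
|---|---|---|---|
| 0.1 | 1.2 | 7.4% | not run |
| 0.3 | 1.6 | 12.1% | 11.8% |
| 0.5 | 2.0 | 16.6% | 16.2% |
| 0.7 | 2.4 | 20.6% | 21.2% |
| 0.9 | 2.8 | 24.2% | 23.9% |

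With the participant as the error unit, simulated size was 4.8% to 5.4% across all settings (15 and 20 per arm, both tests).

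**4. Effect of the matching.** If a share s of the between-person variance is common to the two members of a pair, the factor 1 + 2·rho becomes 1 + 2·rho − 3·s·rho. With s = 0.5 it is 1 + 0.5·rho:

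- rho 0.5: factor 1.25; simulated size 7.9%
- rho 0.7: factor 1.35; simulated size 9.2%

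The inflation would vanish at s = 2/3, where the factor is 1. In the same s = 0.5 simulations, a participant-level test that ignores the pairs had size 1.5% and 1.0%. A participant term without a pair term would therefore be too conservative if the matching works.

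**5. Objective 2, arm-by-time.** The true variance of the contrast is (1 − rho) times the assumed one, so the standard error is too large by 1/√(1 − rho). With no true effect,

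size = 2[1 − Φ(1.96/√(1 − rho))],

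which is 0.56% at rho 0.5, 0.03% at 0.7 and about 0 from 0.8 up. Simulated power at 20 per arm:

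| pre/post rho | where the correct test has 80% | where the correct test has 95% |
|---|---|---|
| 0.5 | 53% | 81% |
| 0.7 | 25% | 53% |
| 0.8 | 8% | 25% |
| 0.9 | 0.3% | 1.7% |

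**The case against.** The strongest reply is that silence is not a defined model. A two-way repeated-measures ANOVA, or a two-way ANOVA on one summary score per person (arm by sex, say), would fit the same words. The sample-size text invokes a pair-matched design, and the stated 15 is reproduced by a paired t-test on 15 pairs. This suggests, without proving it, one value per person with the pair as the unit. On that reading the adherence inflation does not arise.

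This stands as far as intent goes. A reader might infer that the trial will certainly use the wrong error term; the documents do not establish that. But the analysis sentence permits the invalid version as readily as a valid one, and the sizing argument does not carry over. The pairing there is between two people and says nothing about repeated scores from one person. Nor does the paired t-test rescue the plan, because used pre/post within one arm it does not compare the arms.

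Three further limits stand.

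- Over-rejection belongs to the arm main effect. An arm-by-session test of adherence would be conservative under positive correlation.
- A reader might infer that the primary test rejects at several times 5% in any case. With half of the between-person variance shared within pairs it is 8-9%, and the documents give no within-pair correlation.
- A reader might infer that Objective 2 could almost never succeed. That needs a pre/post correlation of about 0.8 to 0.9 or more. Such a value is plausible for body fat and mile time but not documented; at 0.5 the test still has 53% power against 80%.

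**Conclusion.** The point holds as a defect of specification with a material consequence if the plan is followed literally. The same people are measured repeatedly, the named method carries no participant term, and neither the paired t-test nor the pair-matched sizing supplies one.

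The two objectives are affected in opposite directions. The adherence arm effect has a type I error of about 7% to 24% over rho 0.1 to 0.9, less if the pairs share variance. The Objective 2 test loses from about a third of its power (80% to 53% at rho 0.5) to nearly all of it (0.3% at 0.9). The directions need only positive within-person correlation and, for adherence, that pairs share less than two thirds of the between-person variance. The sizes are conditional on the arm-by-time layout and on correlations that the documents do not give.

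Because the primary test is affected, the wording should be settled before the data are analysed.

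**What to change.** In the statistical paragraph of Methods:

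- Replace the two-way ANOVA by a two-way repeated-measures (mixed) ANOVA or a linear mixed model. Use arm, session and arm-by-session as fixed effects, participant as the subject or random effect, and the matched pair as a further random or blocking term.
- Name the HIIT-minus-MCEET contrast, tested against participant- or pair-level variation, as the Objective 1 test.
- For body fat and mile time, test the arm difference in within-participant change, with the pair term retained.
- State what the paired t-test is for, and do not use within-arm tests to compare arms.

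If the named software does not fit a mixed model, an analysis of each participant's mean adherence score and pre/post change, with pairs taken into account, does the same job when data are complete. The mixed model has the advantage of keeping people who miss one of the three questionnaires.

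The cost is wording and slightly more analysis work, with no new data. The adherence comparison will usually have a less favourable standard error than the literal ANOVA would report, but a valid one.

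### Program adherence is primary, but none of its several measures, one of them an enjoyment scale, is designated primary, and the sample size uses an unnamed scale from an enjoyment-titled source

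*Combined protocol and SAP*

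**What the plan says.** The Research Hypothesis section sets the main question: "The study hypothesizes that HIIT group will result in greater program adherence than MCEET". The statistical paragraph of Methods then names the primary outcome and its sizing difference: "The primary outcome variable is the program adherence, with a minimum important difference of 19.6 between HIIT (103.8 ± 9.4". The comparison group there is 84.2 ± 19.1. That paragraph gives no instrument, session or summary score. It goes on: "a minimum of 15 participants is required for an alpha of 0.05 and 95% power", and adds 34% for dropout to reach 20 per group.

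The measures appear earlier in Methods. Participants complete the "physical activity enjoyment scale (PACES) and exercise adherence rating scale (EARS) after the 6th, 9th and 15th session to assess their program adherence". The training paragraphs repeat both scales at the same sessions and add: "Completed questionnaires and the recorded heart rate data saved on Fitbit or a mobile app will be used to confirm program adherence". Heart rate is logged at every session, with the stated aim "to ensure safety and achievement of their targeted heart rate". Weeks two to five are unsupervised, three sessions a week, "in order to examine free-living individuals adhere to two exercise programs".

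The study cited for the 19.6 is listed in References under the title "High-Intensity Interval Training Elicits Higher Enjoyment than Moderate Intensity Continuous Exercise".

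**The concern.** The plan has several candidate measures of its primary outcome and no rule for choosing among them. Two questionnaires at three sessions give six scores, and heart-rate records are a further source. One questionnaire is, by its name, about enjoyment. A person can enjoy a program and still skip sessions, so a PACES difference is not evidence of adherence, yet the plan lists PACES as an adherence measure and would let such a difference be reported under the main hypothesis.

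The sizing has the same gap. The difference and standard deviations have no scale attached, and their source is titled for enjoyment. Nothing links them to EARS or to sessions completed.

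The questionnaires are also tied to sessions. Someone who stops early has no later score, and stopping is itself a form of non-adherence. A late comparison is then made among those who stayed, and recruiting extra people does not remove that bias.

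**Working it through.** **The plan's own sizing.** Inputs (statistical paragraph of Methods): 103.8 ± 9.4 and 84.2 ± 19.1, alpha 0.05, power 95%, dropout 34%. Sidedness is not stated; two-sided is assumed throughout.

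- Difference: 103.8 − 84.2 = 19.6, as stated.
- Paired t-test with 19.1 taken as the SD of the within-pair difference: 19.6/19.1 = 1.03, which needs 15 pairs. This matches the stated 15.
- Two independent groups: pooled SD = √((9.4² + 19.1²)/2) = 15.05; d = 19.6/15.05 = 1.30, which needs 16 (normal approximation) or 17 (t) per group.
- Dropout: 15 × 1.34 = 20.1, matching the stated 20.

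So 15 and 20 can be reached, although the printed effect sizes (d = 1.96, f = 0.8) would give about 8 and 12 per group by the t-test. Every route uses the same 19.6, so none shows that the power applies to adherence.

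**Two scales instead of one.** Assume one group test each on PACES and EARS at two-sided 0.05, with no true difference.

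| Correlation (assumed) | Falsely favours HIIT on at least one | Either direction |
|---|---|---|
| 0 | 1 − 0.975² = 4.9% | 1 − 0.95² = 9.8% |
| 0.3 | 4.8% | 9.5% |
| 0.5 | 4.5% | 9.1% |
| One test only | 2.5% | 5% |

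**Sessions and missing scores.** 5 weeks × 3 = 15 sessions, so session 15 is the last. Weeks two to five give 4 × 3 = 12 unsupervised sessions. Dropout: 0.34 × 20 = 6.8, so up to about 7 per arm lack a session-15 score if all of it falls before then. Scores from session 6 or 9 may still exist. About 20 × 0.66 = 13 per arm remain.

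**What the sample can detect.** Unpaired two-sided t-test at 0.05, with no gain from matching on mile time assumed. CI half-width = t × SD × √(2/n).

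| Primary outcome | n per arm | d, 95% power | d, 80% power | 95% CI half-width |
|---|---|---|---|---|
| Session count (dropouts have a value) | 20 | 1.17 | 0.91 | 2.024 × √(2/20) × SD = 0.64 × SD |
| EARS, after 34% loss | 13 | 1.47 | 1.15 | 2.064 × √(2/13) × SD = 0.81 × SD |

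The documents give no SD for sessions completed. For an assumed SD of 2 to 5 sessions out of 12, the session-count row means a detectable difference of 1.17 × 2 = 2.34 to 1.17 × 5 = 5.85 sessions at 95% power, 0.91 × 2 = 1.82 to 0.91 × 5 = 4.55 at 80%, and a half-width of 0.64 × 2 = 1.28 to 0.64 × 5 = 3.20.

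**The case against.** The plan does name measures and sessions. Methods lists PACES and EARS at sessions 6, 9 and 15 for adherence, and heart-rate records to confirm it. A reader of the statistical paragraph alone might infer that adherence has no measure at all. The rest of Methods does not support that: the fault is several candidates with none designated.

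It is also fair to say that the plan does not propose to judge adherence on PACES alone, since it describes both scales plus heart-rate confirmation. That stands as a description of intent. But with no ranking or combining rule, a result on PACES alone is not excluded.

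A reader might infer that the 19.6 is a PACES score. That is likely from the source's title, but the documents do not say so. The point needs only that the scale is unnamed and not shown to be adherence.

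A reader might also count six scale-by-session tests and quote 1 − 0.975⁶ = 14.1%. The plan specifies a two-way ANOVA with Tukey's post hoc test, not six separate uncorrected comparisons, so that figure does not describe it. The two-scale inflation is modest. The main problem is what is being measured.

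Finally, 7 of 20 is a worst case for timing, and it affects the primary result only if a session-15 score is used. That the missing scores depend on adherence is a reasonable inference, not something the documents state.

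**Conclusion.** The concern holds. The primary outcome has several measures, none designated primary and none combined, and one is by name an enjoyment scale. The 95% power rests on a difference on an unnamed scale from an enjoyment-titled source and is not shown to apply to adherence. As written, the plan could report an enjoyment difference as greater adherence. This should be settled before any outcome data are examined, because it decides what the main hypothesis test is.

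The size is a rise in the chance of falsely favouring HIIT from 2.5% to at most about 4.9%, given one two-sided test per scale and non-negative correlation. Up to about 7 of 20 per arm would lack a session-15 score if all planned dropout precedes it. The documents do not show that the trial is underpowered for adherence, because they give no difference or SD identified as adherence. They show only that the stated power has no demonstrated link to it.

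**What to change.** Name one adherence measure, not PACES, as the single primary outcome.

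- **Preferred:** the number of the 12 unsupervised sessions in weeks two to five with a saved heart-rate record. State what counts as a completed session, and count no record as not done, so that dropouts also have a value. Compare groups once at two-sided 0.05 with a paired or two-sample test in place of the two-way ANOVA for this outcome. A rank or permutation version may suit better, since the count is bounded at 12. Report the difference with a 95% CI.
- **Alternative:** EARS at one named time point. It remains missing for people who stop, unless it is also collected from them.

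Make PACES secondary and label it enjoyment. State that the 19.6-point calculation is not shown to apply to the chosen primary. Replace the 95% power statement with the detectable difference and CI half-width for that choice, using the 20-per-arm row for the session count and the 13-per-arm row for EARS.

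**Cost.** The heart-rate data are already planned for every session and already serve to confirm adherence, so the preferred option needs a written rule rather than new data. Its drawbacks are that device or logging failures count as missed sessions, and that a saved record does not prove the prescribed session was done. Either choice makes the stated power less favourable: the planned sample detects only a large difference.

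### The sample-size inputs contradict each other: 19.1 cannot be a pooled variance, d = 1.96 and f = 0.8 do not describe the same two-group difference, and the powered test is not named

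*Combined protocol and SAP*

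**What the plan says.** The sample size is justified only in the closing paragraphs of Methods. The primary outcome is program adherence, with a "minimum important difference of 19.6 between HIIT (103.8 ± 9.4) and MCEET (84.2 ± 19.1". The text continues "we calculate the pooled variance (19.1), effect size f (0.8" and gives Cohen's "d (1.96) for the sample size estimation".

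The method is described in two ways. First: "Sample size estimates are generated with a two-way analysis of variance (ANOVA". Then: "Using ANOVA, match-paired study design, a minimum of 15 participants is required for an alpha of 0.05 and 95% power". The analyses listed are a two-way ANOVA, Tukey's "post hoc test, and a paired t-test", none of them tied to the primary outcome. A 34% dropout allowance "will be included in addition to the minimal sample size resulting in 20 participants for each group".

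Earlier in Methods, allocation is described as follows: "Participants will be match-paired based on their endurance capacity to either HIIT or MCEET group for five weeks". The enjoyment and adherence questionnaires are completed three times, after sessions 6, 9 and 15.

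The plan does not give the ANOVA factors, the powered effect, a within-pair or within-person correlation, the time point or the sidedness. Nor does it say whether 15 means per group, pairs or total.

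**The concern.** One number appears in two roles. It is the ± value of one group and, a sentence later, the pooled variance of both. The two effect sizes do not match each other through the usual two-group relation, and neither matches the quoted group data under equal weighting. Two descriptions of the test are offered, and they need different inputs.

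This paragraph is the only support for the trial's size and for its 95% power. If the inputs conflict and the test is not named, nobody can reproduce 15, judge whether 20 per group is enough, or tell which analysis of adherence is the primary one.

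**Working it through.** **Inputs, all from the sample-size paragraph:** means 103.8 and 84.2; ± values 9.4 (HIIT) and 19.1 (MCEET); stated pooled variance 19.1, f = 0.8, d = 1.96; alpha 0.05; power 95%; n = 15; dropout 34%; 20 per group.

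**Assumptions, because the plan is silent:** the ± values are SDs, tests are two-sided, and the two variances are equally weighted unless stated otherwise. Power is from the noncentral t or F distribution.

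**1. What 15 refers to.** 15 × 1.34 = 20.1, which matches 20 per group. So 15 is read as per group, or as pairs.

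**2. The pooled variance.**
- 9.4² = 88.36 and 19.1² = 364.81. Any weighted average lies between these, so 19.1 is impossible.
- Equal weighting: (88.36 + 364.81)/2 = 226.6, pooled SD 15.05.

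**3. The effect sizes.**
- From the quoted data: d = 19.6/15.05 = 1.30 and f = d/2 = 0.65.
- Over all weightings, d runs from 19.6/19.1 = 1.03 to 19.6/9.4 = 2.09.
- Stated d = 1.96 implies SD 19.6/1.96 = 10.0. That needs a HIIT weight of (364.81 − 100)/(364.81 − 88.36) = 96%.
- Stated f = 0.8 means d = 1.60 and SD 19.6/1.60 = 12.25. That needs a HIIT weight of (364.81 − 150.06)/(364.81 − 88.36) = 78%.
- Each value is possible alone, but one data set cannot have both weights.

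**4. Do the stated effect sizes give 15?** Sample size for 95% power, with paired effect dz = d/√(2(1 − r)):

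| Stated value | Unpaired, per group | Pairs, r = 0 | r = 0.2 | r = 0.5 |
|---|---|---|---|---|
| d = 1.96 | 8 | 9 | 8 | 6 |
| f = 0.8 (d = 1.60) | 12 | 13 | 11 | 8 |

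None is 15.

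**5. Routes that do reach 15, or come close.** The plan states none of them.
- (a) Paired t-test with 19.1 taken as the SD of within-pair differences: dz = 19.6/19.1 = 1.026. Power is 94.3% at 14 pairs and 95.8% at 15.
- (b) A 2-df term in a 2 × 3 ANOVA (two groups, three assessments) with f = 0.8, treating repeated observations as independent: N = 28 (95.1%), or 30 with equal cells (96.5%), which is 15 per group.
- (c) Two-group normal approximation: 2 × (1.960 + 1.645)² × 226.6/19.6² = 15.3, which rounds up to 16.

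**6. Power from the quoted data, two-group t-test.**

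| Weighting | d | 13 per group | 15 per group | 20 per group | Needed for 95% |
|---|---|---|---|---|---|
| Equal | 1.30 | 89% | 93% | 98% | 17 |
| HIIT weight 1/3 | 1.19 | – | 88% | – | 20 |
| HIIT weight 2/3 | 1.46 | – | 97% | – | 14 |

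The 13 are the completers expected from 20 × 0.66 = 13.2. A simulation with the two unequal SDs (200,000 runs) gave 92–93% at 15 and 98% at 20, so unequal variances do not change the picture.

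**7. Power from the quoted data, paired t-test.** SD of differences = √(9.4² + 19.1² − 2r × 9.4 × 19.1); the plan gives no r, so a range is shown.

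| Assumed r | SD of differences | Power at 15 intact pairs | Pairs for 95% |
|---|---|---|---|
| 0 | 21.29 | 91% | 18 |
| 0.2 | 19.53 | 95% | 15 |
| 0.5 | 16.54 | 99% | 12 |

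**The case against.** The strongest reply is that 15 has not been shown to be wrong. The plan describes a matched-pair design and lists a paired t-test, and with 19.1 as the SD of within-pair differences 15 is exactly the minimum number of pairs. With the quoted SDs and r = 0.2 the answer is again 15. This stands: the printed number may be right with only a label wrong. But the plan calls 19.1 a pooled variance, not an SD of differences, and it attributes the calculation to ANOVA.

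A second reply is that f may belong to an interaction or another multi-df term, for which f need not equal d/2. That is true, and the conflict is claimed only for a two-group contrast. The plan names no such term, and the only effect it states is a single difference between two groups.

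A third is that two-sided testing is assumed although the hypothesis is directional. One-sided, with d = 1.30, 14 per group would suffice, and power would be 96.7% at 15 and 94.3% at 13. Two-sided is the usual default, but the plan should say so. Neither the mislabelled variance nor the conflict between d and f depends on sidedness.

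Finally, 15 might be a total. With d = 1.96 the total is 16 (8 per group), close to 15. The step from 15 to 20 per group argues against that reading.

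**Conclusion.** The point holds. With the ± values read as SDs, 19.1 is not a pooled variance under any weighting. The stated d and f cannot both describe the one two-group difference the plan gives. The powered test and term cannot be identified from the text.

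This is a fault of consistency and traceability, not a large shortfall. For a two-sided two-group test with equal weighting, the requirement before dropout is 17 per group rather than 15, or 14 to 20 if the HIIT weight lies between 2/3 and 1/3. For a paired test, 15 intact pairs give 91% to 99% power for r from 0 to 0.5. It should be fixed, because the 95% claim cannot be verified as written.

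**What to change.** Rewrite the sample-size paragraph:

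- Label 19.1 as the MCEET SD, and state the sidedness and the unit of 15.
- Name the one test, term and time point of the primary outcome that is powered. Give inputs and power for that test only, and do not carry d or f from one test to another.
- If it is a two-group comparison: pooled SD 15.05 (variance 226.6, equal weighting declared as an assumption), d = 1.30, f = 0.65, two-sided power 93% at 15 completers per group, 98% at 20 and 89% at 13.
- If it is a paired comparison: state the assumed SD of within-pair differences or the correlation, and show power over a range. Separately, give power for the number of pairs expected to stay intact, with the assumed dropout pattern.
- If it is a multi-df ANOVA term: name it and derive f from assumed cell means and the within-person correlation.

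The cost is rewording one paragraph and committing to one primary test. Enrolment can stay at 20 per group, but for a two-sided two-group test the plan would then have to report 89% power at the expected 13 completers. Keeping 95% after 34% dropout would need 17/0.66 = 25.8, so 26 enrolled per group. Part of that increase comes from inflating by 1.34 instead of dividing by 0.66, which is a separate matter.
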